A safety rule to stop the trial is to find significant differences in efficacy endpoint or adverse event variables in interim analyses. The significance level established for stopping the test is $p<0.01$ for safety and $p<0.001$ for efficiency(Haybittle-Peto limit)¹³.

If the trial ends early or is suspended for any reason, the investigator shall promptly inform the trial subjects, ensuring appropriate treatment and follow-up of the trial and, where required by applicable law, inform the regulatory authority.

If the investigator terminates or suspends a trial without the prior agreement of the sponsor, he or she shall promptly inform the institution, and the investigator/institution shall promptly inform the sponsor and the CEIm and provide them with written justification for the cause of such termination or suspension.

If the sponsor terminates or suspends a trial, the investigator must inform the Institution where the trial is conducted and the investigator/institution must promptly inform the CEIm by providing written justification of the reasons for the termination or suspension.

If the Ethics Committee (CEIm) terminates or withdraws the favourable opinion of a trial, the investigator shall inform the institution and the investigator/institution shall promptly inform the sponsor of this fact and provide written justification as to the cause of such termination or suspension.

8. Description of the treatment.

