11.3. Statistical analysis

The categorical variables will be presented as frequency and percentage and the continuous variables as mean and standard deviation.

Death after 28 days, intubation or admission to the ICU will be presented as proportions. The difference in proportions will be estimated with a 95% confidence interval.

An analysis per protocol will be performed, considering those patients who have received at least 2 doses of the assigned drug. In addition, an intention-to-treat analysis will be carried out.

In the event that there is a depletion of stock and any of the guidelines are replaced by one of the alternatives proposed in point 8.2, no adjustment would be made in the analysis since the equivalence of dose and dosage between the original dose and the substitution is established.

For the analysis of the main outcome, death at 28 days, survival analysis will be performed and the Hazard ratio of the Cox regression, with the log-rank statistic, will be used to estimate the mortality relationship.

An alpha error of 5% is set.

In case there was a lack of balance in the age of the patients between the groups, age-adjusted analyses would be performed, establishing 2 groups: < 70 years and \geq 70 years.

Two interim efficacy and safety analyses are established with 100 and 200 patients

2 analyses of the results are established according to:

- a) Time of evolution (<7 days from the onset of symptoms, \geq 7 days from the onset of symptoms).
- b) Presence of a state of high inflammation. The patient is considered to have a high degree of inflammation when he meets any of the following laboratory criteria:
 - Ferritin greater than or equal to 1000 mg/dl
 - IL-6 greater than or equal to 20 pg/ml
 - PCR mayor o igual a 150 mg/l
 - D-dimer greater than or equal to 1000 mg/dl

Finally, since no age criterion is established to exclude older patients, a sensitivity analysis will be performed, leaving out those patients who had orders of no intubation or non-invasive mechanical ventilation prior to being included in the study.

For statistical analysis, the IBM SPSS statistics, version 21 program will be used.

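### Age should be in the primary model for 28-day death whatever the balance: adjusting only on an undefined imbalance gives up 0 to about 6 points of power, depending on an age effect the documents do not give

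*Combined protocol and SAP*

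**What the plan says.** Section 11.3 sets the primary analysis: "For the analysis of the main outcome, death at 28 days, survival analysis will be performed and the Hazard ratio of the Cox regression". The accompanying test is log-rank, and no covariate is named. Age is then made conditional: "In case there was a lack of balance in the age of the patients between the groups, age-adjusted analyses would be performed". When it is used, age enters as two classes split at 70 years.

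The same section schedules the interim looks: "Two interim efficacy and safety analyses are established with 100 and 200 patients". Section 7.4 sets the limits for stopping early: p<0.001 on efficacy and p<0.01 on safety. Neither section says whether age adjustment applies at those looks.

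Three other points bear on this. Section 6.1 describes central 1:1 allocation and mentions no stratification factor. Section 11.3 notes that "no age criterion is established to exclude older patients"; the sensitivity analysis attached to that remark removes patients with prior treatment-limitation orders, so it is not an age adjustment. The software is fixed: "For statistical analysis, the IBM SPSS statistics, version 21 program will be used".

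**The concern.** Under randomisation any age imbalance is due to chance, so observed imbalance is the wrong basis for deciding whether to adjust. The gain from adjusting depends on how strongly age predicts death, and it is there whether or not the arms happen to look balanced. The plan itself singles out age as the variable to adjust for and enrols adults with no upper age limit, yet it would normally leave age out of the main analysis.

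The trigger is also undefined. Section 11.3 gives no test, no cut-off and no decision-maker. The natural reading is that the unadjusted result leads and the adjusted one is extra, but the text does not say so. In an open-label trial that leaves some room to choose which result to emphasise after the data are seen. With about 48 deaths expected, a baseline variable already in use could add power at almost no cost.

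**Working it through.** **1. The plan's own figure.** Section 11.1 gives p₁ = 0.23, p₂ = 0.10, alpha 5% (two-sided assumed), power 80%, and 145 per arm. With δ = 0.13 and mean proportion 0.165:

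n = [1.960·√(2·0.165·0.835) + 0.842·√(0.23·0.77 + 0.10·0.90)]² / δ² = (1.029 + 0.435)² / 0.0169 ≈ 127 per arm.

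With continuity correction, (n/4)·[1 + √(1 + 4/(nδ))]² = 142. The stated 145 is therefore reproduced closely.

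**2. Power without age.** At 145 per arm, z = (√145·0.13 − 1.029)/0.517 = 1.04, so power is 85.0%. Expected deaths are 145 × (0.23 + 0.10) = 47.9 at the end, 50 × 0.33 = 16.5 at the look at 100 patients, and 100 × 0.33 = 33 at the look at 200.

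**3. Simulation.** From the plan: 145 per arm, follow-up censored at day 28, mortality 23% and 10% overall (23% in both arms for type I error), and looks at 50, 100 and 145 per arm. Assumed, because the documents give neither an age distribution nor an age effect: age normal with mean 65 and SD 14, truncated to 18–100; age hazard ratio (HR) per decade from 1.0 to 2.2; exponential survival; complete 28-day follow-up at each look. There were 20,000 trials per cell, and the paired simulation error of a gain is 0.1 to 0.2 points.

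The plan's rule was modelled as log-rank unless the trigger fires, then Cox with the 70-year split (score test). Two triggers were tried: p<0.05 for age (fires in about 5% of trials) and standardised difference >0.1 (39–40%).

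**4. Final power (%) and gains (points).**

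| Age HR per decade | 1.0 | 1.3 | 1.5 | 1.8 | 2.2 |
|---|---|---|---|---|---|
| Log-rank | 85.9 | 86.2 | 85.7 | 86.0 | 85.9 |
| Continuous age, score test | 85.8 | 86.9 | 87.5 | 89.6 | 92.1 |
| Gain over log-rank | -0.1 | 0.7 | 1.8 | 3.6 | 6.2 |
| Gain over rule, p<0.05 trigger | 0.0 | 0.7 | 1.6 | 3.3 | 5.7 |
| Gain over rule, standardised difference >0.1 | 0.0 | 0.4 | 1.1 | 2.2 | 4.1 |
| 70-year split always used, gain over log-rank | -0.1 | 0.5 | 1.0 | 2.2 | 3.6 |

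The likelihood-ratio test with continuous age gains 0.1/0.9/2.0/3.7/6.3 points over log-rank.

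**5. Chance of crossing p<0.001 under 23% versus 10% (%).**

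| Age HR per decade | 1.0 | 1.3 | 1.5 | 1.8 | 2.2 |
|---|---|---|---|---|---|
| 100 patients: log-rank | 4.7 | 4.7 | 4.5 | 4.9 | 4.5 |
| 100: score with age | 4.9 | 5.2 | 5.5 | 6.8 | 7.8 |
| 100: Wald with age | 0.4 | 0.4 | 0.5 | 1.0 | 1.6 |
| 200 patients: log-rank | 20.2 | 19.6 | 20.3 | 20.4 | 19.9 |
| 200: score with age | 20.2 | 20.6 | 22.9 | 25.3 | 29.9 |
| 200: Wald with age | 12.7 | 13.2 | 15.0 | 17.5 | 21.4 |

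An adjusted model read off its Wald p-value would nearly disable the first efficacy look, so the test has to be named.

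**6. Type I error.** Score test 4.8–5.2%; log-rank 4.8–5.2%; likelihood-ratio 4.9–5.2%; score test over all three looks combined 4.9–5.3%. At the first look the null crossing of p<0.001 is 0.07–0.14% (score) and 0.09–0.15% (likelihood-ratio). The plan's rule applied mechanically gives 4.0–5.1%. Claiming success on either result when the trigger fires gives 4.8–5.7%. The worst case, where both results always exist, reaches 6.8%.

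**7. Sensitivity.** With age SD 10 the gain over log-rank is 0.7/2.0/3.9 points at HR 1.5/1.8/2.2. At HR 1.8, mean age 60 gives 3.8 and mean age 70 gives 2.9. If the true effect is a step at 70 (HR 3), linear age gains 1.0 and the split 1.5. If risk is flat to age 50 and then curves up to HR 6 at 80, linear age gains 8.2. A separately coded simulation (6,000 to 8,000 trials per setting) gave about 0 for weak effects, 2 at HR 1.5, 4 at HR 1.8, 5.8 at HR 2.0 and 9 at HR 2.5.

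**The case against.** The strongest reply is that nothing is broken. Log-rank is valid, the rule does not inflate type I error, and power already exceeds the 80% target. All of that is right, and it limits the point to an improvement.

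Second, the size has no anchor in the documents. HR 2.2 per decade means 2.2³ ≈ 10.6 times the hazard at 80 as at 50, and the upper figure is simply where the assumed range ends. That also stands. Only the direction is firm, and the gain is nil if age hardly matters.

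Third, the fair comparator is the plan's rule rather than log-rank alone. Against the rule the top figure falls to 5.7 or 4.1 points, which is smaller but not different in kind.

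Fourth, a smaller edit is available: a log-rank test always stratified at 70 keeps the plan's test and cut and raises no score-versus-Wald question. In 4,000 trials per cell it reached 86.3% at HR 1.5 and 89.3% at HR 2.2, against 85.4% and 85.8% for log-rank and 87.0% and 92.1% for continuous age. It is a reasonable second choice, but it recovers only about half the gain (0.9 of 1.6 points and 3.5 of 6.3). It does better than a linear term only if risk really steps at 70.

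Fifth, the Wald problem belongs to the proposed model, not to the plan. Agreed: it is a reason to word the change carefully, not evidence against Section 11.3.

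Last, the room for selective emphasis is slight. The two results fall on opposite sides of p=0.05 in only 0.1–0.7% of trials (p<0.05 trigger) or 0.5–3.5% (standardised difference >0.1).

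**Conclusion.** The concern holds as an improvement that should be made, not as an error that invalidates the analysis. Always adjusting for continuous age gains from about 0 to 6.2 points of final power over log-rank, and from about 0 to 4.1–5.7 points over the plan's rule, with type I error unchanged. The range rests on assumed values: age mean 65, SD 14, and an age HR per decade of 1.0 to 2.2. Six points is not a ceiling, and a narrower age spread shrinks the gain. Apart from power, the change removes an undefined decision from the primary analysis. Anyone unconvinced by the power gain should still define or delete the trigger and say which result leads.

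**What to change.** In Section 11.3, state that:

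- the primary Cox model for 28-day death contains treatment and age as one continuous linear term, whatever the observed balance, at both interim looks and at the final analysis;
- treatment is tested by the score test from that model (the age-adjusted counterpart of log-rank), not the Wald test, and this p-value is compared with the p<0.001 efficacy limit and with the final 5% level;
- the unadjusted hazard ratio and log-rank test are supportive, and the split at 70 is descriptive.

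Delete the imbalance trigger. Before the analysis is fixed, confirm that SPSS 21 prints this score statistic. If it does not, name the likelihood-ratio test instead: twice the log-likelihood difference between the age-only and the age-plus-treatment models. It performs almost identically.

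The cost is two or three sentences. No new data should be needed, since Section 11.3 already relies on age, and the sample size is unaffected. The hazard ratio must then be read as conditional on age. One linear term keeps the model small at the first look, with about 17 expected deaths. Whether the per-protocol or the intention-to-treat analysis is primary is a separate question that this change does not settle.

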11.4. Responsibilities

- Coordination between the different groups for data management tasks is the responsibility of the promoter.
- Only authorised and adequately trained persons shall have access to the electronic data collection system.
- Data controllers shall ensure access to the system to all authorised persons.
- The promoter shall be responsible for the consistency of the eCRD data against the source data.

- Verification of eCRD data and source data will be the responsibility of the study monitor or, failing that, of the sponsor.

12. Security Assessment.

12.1. Definitions.

- **Adverse Event (AA):** An adverse event is any unwanted medical reaction experienced by the patient at any time during the course of the study, whether or not considered related to the study treatment. This definition includes the development of a new disease and the exacerbation of pre-existing disorders other than the indication under study.
- **Adverse Reaction (AR):** An RA is any harmful and unintended reaction to an investigational drug, regardless of the dose administered.
- **Serious Adverse Event (SAA) and Serious Adverse Reaction (RAG):** AEs or RAs are considered serious if, at any dose, may result in death, threaten the life of the subject, require hospitalization of the patient or prolong an existing hospitalization, cause permanent or significant disability or disability, or result in a congenital anomaly or malformation. Suspicions of medically important AA or RA are also considered serious, even if they do not meet the above criteria, including important medical events that require intervention to prevent one of the consequences described above from occurring. In addition, all suspected transmission of an infectious agent through a medicinal product shall be reported as serious.

The concept "threatening the life of the subject" in the definition refers to the fact that, in the opinion of the researcher, the patient at the time of AA or RA is at real risk of death; it does not mean that AA/RA hypothetically could have caused death if it had been more intense.

The concept of "requiring hospitalization" will exclude both hospitalizations planned for scheduled treatments and those that have been planned or anticipated before the study begins in relation to a pre-existing medical condition.

- **Unexpected Adverse Reaction (RAI):** Any RA whose nature, intensity or consequences do not correspond to the reference safety information.
- **Unexpected Serious Adverse Reaction (RAGI):** AGR (previously defined), the nature, severity or consequences of which do not correspond to the reference safety information.

12.2. Causality Criteria

- **Related OA:** The temporal relationship of AA to the medication under study indicates a possible causal relationship and cannot be explained by factors such as the patient's clinical status, therapeutic interventions.
- **Unrelated OA:** The temporal relationship of AA with study medication indicates an unlikely causal relationship, or other factors (medication or concomitant conditions), other therapeutic interventions provide a satisfactory explanation for AA.

12.3. Reference Security Information

In this study the reference safety information (SRI) will be the information available in the corresponding Summary of Product Characteristics of the drugs under study:

1. RECOVERY guideline. Intravenous administration of 6mg of dexamethasone every 24h for 10 days. It can be given both orally and intravenously at the same dose.
2. BOWLING GUIDELINE. Intravenous administration of 250mg of methylprednisolone every 24 hours for 3 days.

12.4. Security variables and parameters

The assessment of the safety of the drugs under study will be carried out through clinical examination (physical, analytical and / or radiological) and by collecting serious adverse effects and those that may be directly related to the medication under study, such as:

- Nosocomial infection (superadded infection developed at least 3 days after administration of the first dose of steroids) with microbiological confirmation by

culture. When there is no microbiological confirmation, the diagnosis is established at the discretion of the physician.

- Hyperglycemia in non-diabetic patients or decompensation of diabetes mellitus in previously controlled patients. To define this event, the presence of at least one glycemic value greater than 180 mg/dl in the laboratory at any point of evolution or a value greater than 150 mg/dl in fasting capillary glycemia during the days that the patient receives treatment with glucocorticoids is established.
- Episodes of psychosis defined as the presence of euphoria, behavioral changes, aggressiveness, alteration of thought with disorganization of this or presence of hallucinations or delusions.
- Any other treatment-related adverse reactions that, in their medical judgment, are relevant to the safety of the study drug.

12.5. Information on Adverse Events

All adverse events shall be recorded in the data collection log. For each adverse event, the start and resolution dates, intensity, duration and consequence on study treatment (e.g. discontinuation) will be recorded. The severity of the adverse event and its relationship to the study will be assessed according to specific guidelines. Any action taken or results obtained (e.g. hospitalisation, withdrawal of treatment, etc.) will also be recorded.

The investigator or a collaborator will question and/or examine the subject in relation to the incidence of adverse events.

Adverse events will be collected once the subject has been recruited. If a subject suffers an adverse event after signing the informed consent document (inclusion), but before assigning the treatment (recruitment), the event will NOT be recorded unless the researcher considers that it has a causal relationship with some procedure of the protocol.

Over the course of the study, the facility staff will again note any changes that occur in the disorder and nature of the possible adverse events.

12.6. Assessment of the intensity of adverse events and their relationship to treatment

The following definitions shall be applied to assess the intensity of adverse events:

- Mild: the sign, symptom or event is known, but it is easily tolerated.
- Moderate: there is enough discomfort to interfere with usual activity and may warrant intervention.
- Severe: it is disabling and produces inability to perform usual activities or significantly affects the clinical state and warrants intervention.
- Life-threatening: immediate risk of death.
- Death

12.7. Assessment of the imputability of adverse events and serious adverse events with the study treatment: Imputability criteria.

The sponsor will classify adverse events, based on their causal relationship with the drug, according to the Karch and Lasagna Algorithm (1977), as:

- **Definitive:** there is a reasonable time sequence between the administration of the drug and the appearance of AA. This event coincides with the RA described for the drug, improves with its suppression, reappears after its readministration and cannot be explained by alternative causes.
- **Probable:** there is a reasonable time sequence between the administration of the drug and the appearance of AA. This event coincides with the ARs described for the drug, improves after discontinuation of treatment and cannot be explained by other alternatives.
- **Possible:** there is a reasonable time sequence between the administration of the drug and the appearance of AA. This event coincides with the RA described for the drug but can be explained by alternative causes.
- **Conditional or Unlikely:** there is a reasonable temporal sequence between the administration of the drug and the appearance of AA. This event does not coincide with the RA described for the drug and can be explained by alternative causes.
- **Unrelated:** there is no reasonable time sequence between the administration of the drug and the appearance of AA. This event does not coincide with the RA described for the drug and can be explained by alternative causes.

For expedited notification purposes, the definitive, probable and possible categories of Karch and Lasagna's (1977) algorithm will be considered as related and the conditional or improbable category of said algorithm as unrelated.

The determination of the possible relationship with the treatment of the study is the responsibility of the principal investigator of the research center or the person designated by it and, once notified, will be reviewed by the sponsor of the study and / or person to whom it delegates.

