12.9. AAG Notification, Expedited Notification, and Pregnancy Notification

Although the safety data collected in the corresponding Summary of Product Characteristics of the investigational drugs indicate their tolerance profile, the limited data on the doses used in this study make us take measures to control the safety of the product. Therefore, any adverse event that meets the severity criteria defined throughout the study follow-up will be collected and reported.

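### The expedited-reporting rule in 12.7 builds expectedness into relatedness, so a serious event of a new kind can lose its individual RAGI report

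*Combined protocol and SAP*

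**What the plan says.** Section 12.7 grades causality in five steps and then reduces them to two for expedited reporting: "For expedited notification purposes, the definitive, probable and possible categories" of the algorithm "will be considered as related and the conditional or improbable category of said algorithm as unrelated".

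The three grades that count as related share one condition:
- Definitive: "This event coincides with the RA described for the drug, improves with its suppression", and it also recurs on re-exposure and has no other explanation.
- Probable: "This event coincides with the ARs described for the drug, improves after discontinuation of treatment", with no other explanation.
- Possible: "This event coincides with the RA described for the drug but can be explained by alternative causes".

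The conditional or unlikely grade is for an event that has plausible timing, does not match a described reaction, and could have another cause.

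Four other places bear on this:
- Section 12.1 defines an unexpected reaction as "Any RA whose nature, intensity or consequences do not correspond to the reference safety information". A RAGI is the serious form. Section 12.3 names the Summary of Product Characteristics as the reference safety information.
- Section 12.2 gives a separate two-level test. An event is related if its timing "indicates a possible causal relationship and cannot be explained by factors such as the patient's clinical status" or by other therapeutic interventions. This test does not require the reaction to be described already.
- Section 12.10.1 sends RAGIs to the agency and the regions within 15 calendar days, or within 7 if fatal or life-threatening.
- Section 12.9 explains why serious events are collected: "the limited data on the doses used in this study make us take measures to control the safety of the product".

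**The concern.** Expedited reporting rests on two separate questions: could the drug have caused the event, and was a reaction of this kind already known? A RAGI needs yes to the first and no to the second. Section 12.7 answers the first question partly by means of the second. An event of a kind not yet described fails the relatedness rule because it is new, although newness of that sort is one of the three ways in which 12.1 lets a reaction be unexpected.

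What is at stake is the individual, time-limited report to the authorities on a new type of serious harm, in a trial whose own protocol says that data on the doses used are limited.

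**Working it through.** No arithmetic is needed beyond counting cases. The inputs are the grade definitions and the mapping sentence in 12.7, the definitions in 12.1, the test in 12.2, and the time limits in 12.10.1 and 12.10.2.

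**Step 1: the distinct cases.** Assume plausible timing and apply the 12.7 definitions as worded.

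| Event | 12.7 grade | For expedited notification | Under 12.2 |
|---|---|---|---|
| Described, no other cause, improves and recurs | Definitive | Related | Related |
| Described, no other cause, improves, no recurrence shown | Probable | Related | Related |
| Described, no other cause, does not improve | None | Not stated | Related |
| Described, another cause could explain it | Possible | Related | Unrelated if that explanation is satisfactory |
| New, another cause could explain it | Conditional or unlikely | Unrelated | Unrelated if that explanation is satisfactory |
| New, no other cause | None | Not stated | Related |

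Of the 6 cases, 3 are related, 1 is unrelated and 2 have no grade (3 + 1 + 2 = 6). Of the 2 new cases, 0 reach related. Crossing all four yes/no criteria gives 16 combinations, 8 of them undescribed. But improvement and recurrence play no part in grading an undescribed event, so those 8 are two cases counted four times each.

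**Step 2: against the RAGI definition.** Section 12.1 allows a reaction to be unexpected in nature, intensity or consequences. Under 12.7 a described reaction can be related and still be unexpected in intensity or consequences. A reaction new in nature has no route to related.

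**Step 3: the gap for described reactions.** A fatal reaction cannot improve on stopping. If it is described and another cause is conceivable, it is possible, hence related. If no other cause is conceivable, it has no grade. The less ambiguous case is the one left out.

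**Step 4: against 12.2.** The two sections part most clearly on a new event with no other cause (related in 12.2, ungraded in 12.7) and on the described event of step 3 (likewise). They may also part on a described event with a rival explanation. There the thresholds differ: 12.2 asks for a satisfactory explanation, while 12.7 asks only whether one is available. The same event therefore need not get opposite answers.

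**Step 5: what remains if the RAGI report is lost.**
- 12.10: every serious event goes to pharmacovigilance within 24 hours, whatever its relatedness or expectedness.
- 12.10.2: information that could change the benefit/risk balance is notified within 15 days.
- 12.11: annual reports include serious adverse events as well as RAGIs.
- 12.12: investigators receive safety information that could affect patients as soon as possible.

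None of these restores the individual RAGI report. For a fatal or life-threatening event, the benefit/risk route has a limit of 15 days instead of 7, a difference of 15 − 7 = 8 days, and it depends on a separate judgement that the balance could change.

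**The case against.** A reader might infer that a serious reaction of unexpected nature can never become a RAGI. The documents do not go that far:
- The definition of an adverse reaction in 12.1 does not require it to be described, and the RAGI definition builds on that one.
- The end of 12.7 makes the principal investigator, or a delegate, responsible for judging the relationship, with sponsor review. It does not confine that judgement to the algorithm.
- A new event with no other cause is ungraded, not labelled unrelated, and 12.2 would call it related.
- Section 12.7 does not tie described to the Summary of Product Characteristics. A reaction described elsewhere but absent from that summary could be both related and unexpected.

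A reader might also infer that feedback to investigators fails. It does not: 12.12 sets no condition on relatedness or RAGI status.

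The appeal to limited dose data in 12.9 has limits too. A natural dose concern is a known reaction in a worse form, and the rule lets those through, apart from the gap in step 3. Finally, the text reads as a machine translation and summarises a published algorithm that is not reproduced, so a clause-by-clause reading calls for some caution.

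All of this stands as a limit on the point. It does not remove the defect. Section 12.7 is the only text that says how relatedness is decided for expedited notification. It expressly maps a new event with a conceivable other cause to unrelated, and 12.2 does not rescue that case. For the ungraded cases, staff have two sections that differ and no rule on which prevails.

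**Conclusion.** The wording of 12.7 is wrong for its purpose and should be changed. For expedited notification it makes relatedness depend on prior description, which conflicts with the RAGI definition in 12.1 and, for events with no other cause, with 12.2.

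The consequence is bounded. Novel serious events are still captured and have other ways to reach the authorities and investigators. What can be lost is the individual report within 15 calendar days, or 7 if fatal or life-threatening.

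The documents give no basis for predicting how many events would be affected, and the count of cases in 12.7 says nothing about frequency. In patients hospitalised with COVID-19 another cause can often be proposed, which would send a new event to unrelated. That is a judgement, not a figure from the plan.

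The conclusion assumes that staff apply the 12.7 definitions as written. If they rely on 12.2 or on clinical judgement instead, fewer reports are lost, but the protocol then does not say which rule was used.

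**What to change.** Four changes to wording:
1. Replace the last sentence of the 12.7 grading text. For expedited notification, an event is related if the timing is reasonable and the investigator or the sponsor considers a causal relation at least a reasonable possibility, whether or not such a reaction has been described.
2. State that expectedness is judged in a separate second step, against the reference safety information in 12.3.
3. State that a serious event with reasonable timing that fits no 12.7 grade is handled as related.
4. Align 12.2 with this, so that one causality test applies throughout.

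The cost is a protocol wording change, a line on the notification form and a few more expedited reports. Design, sample size and treatment are untouched.
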